### **10.3.2. Treatment Group Comparability**

#### **10.3.2.1. Patient Disposition**

A detailed description of patient disposition will be provided at the end of the study.

Frequency counts and percentages of all patients entered, randomized/enrolled, completing, and/or discontinuing from the study early will be presented for each treatment. The reasons for discontinuation from the study will be summarized by treatment group. A summary of discontinuations will also be presented by visit.

#### **10.3.2.2. Patient Characteristics**

Demographic and baseline characteristics will be summarized by treatment. For continuous measures, summary statistics will include sample size, mean, median, maximum, minimum, and SDs along with ANOVA's p-value to test overall treatment effect. For categorical measures, summary statistics will include sample size, frequency, and percent.

#### **10.3.2.3. Concomitant Therapy**

The prespecified concomitant medications of interest will be summarized by treatment.

#### **10.3.2.4. Treatment Compliance**

Treatment compliance is defined as taking at least 75% of required injections for the prespecified time intervals (see Section 7.6). Overall compliance is defined as being at least 75% compliant with investigational product across the treatment period. Compliance will be summarized by each treatment and time interval, and overall. Listings will also be produced.

### **10.3.3. Efficacy Analyses**

#### **10.3.3.1. Primary Analyses**

The primary analysis for the primary endpoint, change from baseline in HbA1c at 18 weeks, will employ MMRM described in Section 10.3.1 in ITT population by censoring all post rescue data.

#### **10.3.3.2. Secondary Analyses**

##### **10.3.3.2.1. Secondary Analyses for Primary Endpoint**

A Bayesian integrated 2-component prediction (ITP) model (Fu and Manner 2010) will be applied as a supportive analysis for the primary endpoint, change from baseline in HbA1c at 18 weeks, in ITT population by censoring all post-rescue data. Probabilities based on posterior distributions of the parameter of interest will be generated from this model. Non-informative priors will be used in this model. In addition, the informative priors from the posterior for placebo and posterior for dulaglutide 1.5 mg obtained from Studies GBCF and H9X-MC-GBDE (GBDE) will be evaluated in this model to check the robustness of the analysis. The primary analysis model, MMRM, will be repeated using the PP and Completers populations for the primary endpoint only to check the sensitivity of the analysis. If the conclusions differ from that of the ITT population, the data and analyses may be further explored using selected pattern mixture models for missing data (Kenward and Rosenkranz 2011). As a sensitivity analysis, the primary endpoint will be analyzed with MMRM and Bayesian ITP model in the ITT population including post-rescue therapy data.

##### **10.3.3.2.2. Analyses for Secondary Efficacy Endpoints**

The ITT population without post-rescue data is the analysis population for secondary efficacy endpoints. The MMRM described in Section 10.3.1 will be used for the secondary continuous efficacy endpoints. For percentages of patients achieving HbA1c target <7.0%, repeated measures logistic regression with generalized linear mixed model described in Section 10.3.1 will be fitted.

A Bayesian ITP model will be fitted to analyze body weight change from baseline as a supportive analysis.

##### **10.3.3.3. Tertiary/Exploratory Efficacy Endpoints**

The analysis of patients reaching HbA1c target  $\leq 6.5\%$  will use the same model as that for HbA1c target <7.0% described in Section 10.3.3.2.2.

Longitudinal continuous variables such as fasting glucagon will be analyzed using MMRM described in Section 10.3.1. If the normality assumption is violated, appropriate transformation is needed prior to analysis.

Non-longitudinal continuous variables such as 6-point SMPG, HOMA-IR, and HOMA-%B will be analyzed using last observation carried forward (LOCF) by fitting a linear model with pooled country, treatment, baseline HbA1c strata as fixed effect, and corresponding baseline value as a covariate. Data transformation may be applied if data are not normally distributed.

### **10.3.4. Safety Analyses**

The safety analyses will include AEs, SAEs, and TEAEs, defined as postbaseline events that are new events or preexisting conditions that worsened in severity after randomization, hypoglycemic and hyperglycemic episodes, and laboratory analytes. Unless otherwise specified, the ITT population will be used for analyses of safety measures.

#### **10.3.4.1. Study Drug Exposure**

Exposure will be calculated for each patient and summarized by each treatment group.

#### **10.3.4.2. Adverse Events**

Adverse events will be coded from the actual term using the Medical Dictionary for Regulatory Activities (MedDRA) and reported with preferred terms and system organ class. Selected notable AEs of interest may be reported using high-level terms.

Summary statistics will be provided for overall AE, TEAEs, SAEs, and study discontinuation due to AEs or death during the treatment period. Counts and proportions of patients experiencing AEs will be reported for each treatment. Adverse events will be analyzed as described in Section [10.3.1](#).

Listings of patients experiencing SAEs, allergic and hypersensitivity reactions, ADA as well as those discontinuing the study, or study medication due to AEs, will be generated.

#### **10.3.4.3. Hypoglycemic Episodes**

Section [9.2.2.1](#) contains definitions of categories of hypoglycemia. A listing of individual hypoglycemic episodes by patient will be presented. Summary reports will include both incidence and rates of hypoglycemia. Hypoglycemia will be analyzed as documented symptomatic, asymptomatic, probable, severe, or nocturnal and for all events combined as total hypoglycemia. Other categories, including the categories above defined with different glucose thresholds, may also be included in these analyses when deemed appropriate.

The incidence will be analyzed using the categorical methods described in Section [10.3.1](#) and rate of hypoglycemic episodes will be analyzed using a generalized linear mixed-effects model assuming negative binomial distribution for hypoglycemic episodes. Incidence and rates will be summarized for each treatment arm and entire treatment period.

#### **10.3.4.4. Severe, Persistent Hyperglycemia**

Listings and summaries (if appropriate) will be provided for events of severe, persistent hyperglycemia resulting in initiation of rescue therapy.

#### **10.3.4.5. Pancreas Safety**

Listings and summaries of adjudicated pancreatic events will be provided.

#### **10.3.4.6. Cardiovascular Safety**

Listings and summaries of adjudicated CV events will be provided. Summaries and listings of supraventricular arrhythmias and cardiac conduction disorders will be provided.

**10.3.4.7. Thyroid Safety**

Listings and summaries of AEs of interest associated with the thyroid gland (benign and malignant neoplasms) will be produced, as well as a listing of biopsy reports.

**10.3.4.8. Renal Safety**

To assess renal safety, summary and analyses, including shift tables, will be provided for renal functional laboratory variables. Listing of AEs suggestive of acute and chronic kidney failure will also be provided. Other reports may also be generated if deemed appropriate.

**10.3.4.9. Gastrointestinal Safety**

Because GI AEs, including nausea, vomiting, and diarrhea, are among the most common events reported in patients treated with dulaglutide, summaries and analyses for incidence, time to onset, duration, and severity of nausea and vomiting will be provided for each treatment during the 18-week treatment period and during the first 6 weeks (titration phase), overall and by visit, to compare the effects of the 4 different dose escalations (2 algorithms for each of the 2 investigational doses) and effects of the 2 titration algorithms on GI tolerability, as well as the overall effects of randomized therapies. The planned reports will be further described in the statistical analysis plan (SAP).

**10.3.4.10. Allergic/Hypersensitivity Reactions**

Summaries and listings of allergic and other hypersensitivity AEs including injection site reaction will be provided.

**10.3.4.11. Immunogenicity**

Summaries and listings of dulaglutide ADA will be generated.

**10.3.4.12. Laboratory Analyses**

Laboratory measurements will be listed by patient. Additional listings will be presented for laboratory measurements that are outside the normal range and for measurements outside certain prespecified clinically relevant thresholds.

Laboratory safety measurements will be summarized. For continuous (numeric) laboratory analytes, the change from baseline to endpoint (Week 18) will be analyzed as detailed in Section [10.3.1](#).

For subjective (qualitative) laboratory analytes, counts and percentages of patients with normal and abnormal values will be analyzed using Chi-square tests or Fisher's exact test.

Shift tables of the change from baseline value to the most extreme postbaseline value, and from baseline to Week 18 for selected analytes using clinically meaningful thresholds will be summarized separately using generalized McNemar's test for within-treatment comparison and using likelihood ratio test for between-treatment comparisons.

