### 10.3. Statistical Analyses

#### 10.3.1. General Statistical Considerations

Statistical analysis of this study will be the responsibility of Lilly or its designee. Any change to the data analysis methods described in the protocol will require an amendment ONLY if it changes a principal feature of the protocol. Any other change to the data analysis methods described in the protocol, and the justification for making the change, will be described in the

clinical study report (CSR). Additional exploratory analyses of the data will be conducted as deemed appropriate.

Unless otherwise specified, listings will include all randomized patients. Efficacy and safety analyses will be conducted in the intent-to-treat (ITT) population. The primary efficacy measure (change from baseline in HbA1c) will also be evaluated in the PP population and Completer sets. In all efficacy and hypoglycemia analyses, all data after rescue therapy will be censored. Analyses of safety parameters, except for hypoglycemia events, will be conducted in the ITT population including the post-rescue therapy data.

Countries with fewer than 10 randomized patients will be pooled for statistical analyses. Pooled country will be employed for all formal statistical model-based analyses.

Unless otherwise specified, all tests of treatment effects will be conducted at a 2-sided alpha level of 0.05, and confidence intervals (CIs) will be calculated at 95%, 2-sided. All tests of interactions between treatments and factors of interest will be conducted at a 2-sided alpha level of 0.10.

The baseline visit will be Visit 3. For all variables, including HbA1c, if baseline data are not available or are missing, the last nonmissing measurement taken prior to this visit will be used for the baseline measurement. The measurement for the primary analysis is defined as the change from baseline in HbA1c to Week 18 (Visit 12).

For all statistical analyses, missing data will be treated as missing at random; therefore, no imputation is needed unless otherwise stated.

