No adjustments for multiplicity will be performed.

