6.13.4.3. Pancreatitis

Summaries of adjudicated and investigator-reported pancreatic events will be provided by each randomized treatment. However, the summary report will only be generated if more than 3% patients have pancreatic event(s). Determination of investigator-reported events will be through the “Acute pancreatitis” Standardized MedDRA Queries (SMQ) and a “Chronic pancreatitis” Lilly Search Categories (LSC) of the AE database, while adjudication-confirmed pancreatitis will be found from adjudication CRF.

The patients developing pancreatitis will be listed separately for the investigator-reported and the adjudicated events.

Each pancreatic enzyme at Week 6 and Week 18, and the maximum post-dose value will be summarized by each randomized treatment, dulaglutide 3.0 mg/algorithm 1, dulaglutide 3.0 mg/algorithm 2, dulaglutide 4.5 mg/algorithm 1, dulaglutide 4.5 mg/algorithm 2, algorithm 1, and algorithm 2 in a shift table using >1 upper limit normal (ULN), and ≥ 3 ULN separately for the ITT population, ITT population with normal baseline, ITT population with baseline value $>$ ULN.

A MMRM with pooled country, baseline HbA1c strata, treatment, visit, and treatment-by-visit interaction as fixed effects will be fitted to analyze each pancreatic enzyme (p-amylase and lipase). In this model, the log transformed ratio (post first dose measure/baseline measure) will be the response variable and log transformed baseline measure instead of baseline measure will be a covariate. The variance-covariance structure selection is detailed in Section 6.1. The treatment in the model will include placebo, dulaglutide 1.5 mg, dulaglutide 3.0 mg/algorithm 1, dulaglutide 3.0 mg/algorithm 2, dulaglutide 4.5 mg/algorithm 1, dulaglutide 4.5 mg/algorithm 2. The report from this analysis will include:

- 1) Geometric LS means and corresponding 95% CIs for each randomized treatment at each scheduled visit, and the ratio in geometric LS means, corresponding 95% CI along with p-value compared relative to placebo and to dulaglutide 1.5 mg at the same visit.

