6.13.10. Clinical Laboratory Evaluation

Amylase, lipase, calcitonin, eGFR, creatinine, urine ACR are included in Section 6.13.4.3, Section 6.13.4.4, and Section 6.13.8. For other laboratory safety measurements summaries will be provided in this Section. For continuous (numeric) laboratory analytes, the rank on the change from baseline to endpoint (Week 18) will be analyzed as detailed in Section 6.1. For qualitative laboratory analytes, the number and percentages of patients with normal and abnormal values will be analyzed using Chi-square tests or Fisher's exact test.

A summary report and analysis for treatment-emergent abnormal laboratory values (outside the reference ranges as appropriate) will be provided for each continuous analyte by treatment. Shift tables of the change from baseline value to the maximum post baseline value to Week 18 for selected analytes using clinically meaningful thresholds will be summarized separately using generalized McNemar's test for within-treatment comparison and using likelihood ratio test for between-treatment (randomized) comparisons. A shift table for ALT, AST, ALP, GGT, total bilirubin, and direct bilirubin will be generated using cutoff \leq 1ULN, (> 1 ULN and < 3 ULN), (≥ 3 ULN and < 5 ULN), (≥ 5 ULN and < 8 ULN), ≥ 8 ULN.

Laboratory measurements will be listed by patient. Additional listings will be presented for laboratory measurements that are outside the normal range and for measurements outside certain prespecified clinically relevant thresholds if deemed appropriate. A listing of patients with either AST or ALT ≥ 3 xULN, and total bilirubin ≥ 2 X ULN will also be provided.

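### For pancreatic amylase and lipase, the protocol's within-arm McNemar rule would compare one baseline value with the maximum of two or three later values, which is not a valid test of no shift

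*Protocol*

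**What the plan says.** Protocol 10.3.4.12 (Laboratory Analyses) plans two kinds of shift table. The first is described as "Shift tables of the change from baseline value to the most extreme postbaseline value". The second uses a fixed visit instead of an extreme, in the words "and from baseline to Week 18 for selected analytes using clinically meaningful thresholds". For both it names "generalized McNemar's test for within-treatment comparison and using likelihood ratio test for between-treatment comparisons". It does not list the selected analytes. Protocol 10.3.1 sets the level ("all tests of treatment effects will be conducted at a 2-sided alpha level of 0.05") and adds "No adjustments for multiplicity will be performed". It defines baseline as one value: Visit 3, or the last earlier value if that is missing.

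SAP 6.13.10 has its own version, "Shift tables of the change from baseline value to the maximum post baseline value to Week 18", with the same tests. Before that it sends amylase, lipase, calcitonin, eGFR, creatinine and urine ACR to their own sections.

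SAP 6.13.4.3 covers the enzymes: "Each pancreatic enzyme at Week 6 and Week 18, and the maximum post-dose value will be summarized". This is a shift table with cut-offs at ULN and 3 times ULN, given for the whole ITT population and separately for patients with normal and with raised baseline. The section names no test for the table. Its formal analysis is an MMRM on the log ratio to baseline.

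**The concern.** McNemar's test asks whether the before and after categories have the same marginal distribution. That describes no drug effect when one value is compared with one value. The larger of two or three values exceeds a single value more often than it falls short of it, by chance alone. If the protocol's rule is applied to the enzyme maximum, the null hypothesis is false before any drug is given, and nearly all false rejections point toward worsening.

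Enzymes matter here. Protocol 3.2 lists short-term effects on pancreatic enzymes among the reasons for the early discontinuation of the 3.0 mg arm in a previous study. Protocol 5.4 says the repeated draws are there to understand enzyme changes at the two investigational doses. A row of small within-arm p-values at 3.0 and 4.5 mg could be misread as a signal.

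**Working it through.** **Which analytes are affected.** Scheduled post-baseline draws in the Schedule of Activities and SAP Appendix 1:

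- Chemistry (with liver tests), hematology, urinalysis, ACR, eGFR and fasting lipids: one (Visit 12 or ET).
- Calcitonin: one in the Schedule of Activities and Protocol 9.2.2.3. SAP Appendix 1 also names serum calcitonin in the amylase/lipase row, but no Week 6 sample is scheduled.
- Pancreatic amylase and lipase: two up to Week 18 (Visits 6 and 12), three if Visit 801 (Week 22) counts. The SAP 6.13.4.3 wording for the maximum has no Week 18 limit, and Appendix 1 gives these enzymes a follow-up window.

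So the most extreme scheduled value differs from the Week 18 or ET value only for the two enzymes.

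**Inputs.** From the documents: two-sided alpha 0.05; 300 / 4 = 75 randomized per arm; 75 × 0.8 = 60 completing. Assumed, because the documents do not give them: prevalence p above ULN at any one visit (5-20%) and between-visit correlation ρ on a latent normal scale (0.7, with 0.5 and 0.9 as alternatives). All values are taken as present.

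**Formulas.** Let c satisfy P(Z > c) = p. Given a patient effect u ~ N(0,1), the chance of being above ULN at a visit is q = Φ((√ρ·u − c)/√(1 − ρ)). With k post-baseline values and no drug effect:

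- P(normal at baseline, maximum abnormal): π01 = E[(1 − q)(1 − (1 − q)^k)]
- P(abnormal at baseline, maximum normal): π10 = E[q(1 − q)^k]
- π01 − π10 = E[1 − (1 − q)^k] − p, which is zero only when k = 1.

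McNemar's statistic is (b − c′)²/(b + c′), where b and c′ are the two discordant counts; it rejects at 3.84 or more. Rejection rates come from numerical integration over u and exact binomial enumeration of b and c′.

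**One case in full** (p = 20%, ρ = 0.7, n = 60):

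- k = 1: π01 = π10 = 0.087; rejection 4.3%.
- k = 2: π01 = 0.141, π10 = 0.054. Expected discordant pairs are 60 × 0.141 = 8.5 against 60 × 0.054 = 3.2. Prevalence of an abnormal maximum is 0.20 + 0.141 − 0.054 = 0.287. Rejection 31.3%.
- k = 3: π01 = 0.180, π10 = 0.039; rejection 67.5%.

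**Null rejection rate (%) at nominal 5%, ρ = 0.7**, each cell giving n = 60 / n = 75:

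| Test | p = 5% | p = 10% | p = 15% | p = 20% |
|---|---|---|---|---|
| k = 1, asymptotic | 3.9 / 4.6 | 4.7 / 4.5 | 4.4 / 4.3 | 4.3 / 4.5 |
| k = 2, asymptotic | 12.2 / 14.6 | 19.2 / 23.1 | 25.4 / 31.7 | 31.3 / 39.6 |
| k = 2, exact | 3.2 / 5.6 | 10.9 / 15.5 | 17.6 / 23.8 | 23.3 / 31.1 |
| k = 3, asymptotic | 26.8 / 32.7 | 44.1 / 53.6 | 57.5 / 68.8 | 67.5 / 78.7 |
| k = 3, exact | 11.2 / 18.3 | 32.0 / 43.1 | 47.2 / 60.0 | 58.3 / 71.3 |

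The plan's own 5% is reproduced when one value is compared with one value, and is lost once a maximum enters.

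**Sensitivity, k = 2, asymptotic.** At ρ = 0.5 and p = 20% the rate is 40.0% / 49.6%. At ρ = 0.9 and p = 5% it is 5.4% / 8.3% (exact 0.5% / 1.1%). A three-category version (Stuart-Maxwell, 4,000 simulated trials per setting, over a range of assumed settings) gave 3.0-4.3% for k = 1, 10.2-53.8% for k = 2 and 22.6-93.9% for k = 3.

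**The case against.** The strongest reply is that where the SAP names McNemar, the fault does not arise, and where it could arise, the SAP names no McNemar test. SAP 6.13.10 removes the enzymes before stating its rule, and the analytes left there have one scheduled post-baseline value. SAP 6.1 keeps unscheduled visits out of summary tables and inference unless otherwise stated, and Appendix 1 keeps one value per window. The renal table in SAP 6.13.8 takes the extreme at baseline as well as after it. Since the SAP names the test in 6.13.8 and 6.13.10, its silence in 6.13.4.3 can be read as making the enzyme table descriptive. All of this stands, and it confines the point to two analytes.

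It does not close the matter. The SAP does not withdraw the protocol's rule for the enzymes. That rule covers undefined selected analytes, and these two are the only laboratory safety analytes for which its most-extreme comparison differs from its Week 18 comparison on scheduled draws.

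Three stronger readings are tempting but not supported:

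- That within-arm shift tests are inflated for laboratory analytes in general. With one scheduled post-baseline value the test holds its level.
- That McNemar will be run in the normal-baseline subset, where every discordant pair must point the same way. No passage plans this.
- That the benefit/risk decision would turn on the result. Placebo would tend to show the same spurious shift, Week 6 and Week 18 enzyme shifts are also tabulated, and the interim criteria in SAP 6.16.2.2 do not use this p-value.

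**Conclusion.** The point holds for pancreatic amylase and lipase only, as an ambiguity between protocol and SAP that would give an invalid within-arm p-value if resolved the wrong way. At an assumed correlation of 0.7 and 5-20% prevalence above ULN, with 60-75 patients per arm, false rejection is about 12-40% with two post-baseline values (exact test 3-31%) and 27-79% with three (exact 11-71%), against 4-5% with one (asymptotic). The three-value figures apply only if Week 22 enters the maximum.

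These sizes rest on the assumed prevalence and correlation. If abnormality is rare and correlation very high, inflation can be negligible. If values at or above 3 times ULN are rarer than those above ULN, inflation at that cut-off would be smaller.

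Severity is minor. The enzyme MMRM against placebo and 1.5 mg is unaffected. The between-arm likelihood-ratio test is not biased by taking a maximum, because all arms share one sampling schedule. No decision rule uses the within-arm result.

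**What to change.** In Protocol 10.3.4.12 and SAP 6.13.4.3, state that for amylase and lipase:

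- within-arm generalized McNemar applies only to fixed-visit shifts, baseline to Week 6 and baseline to Week 18, in the full ITT population;
- the maximum-value shift table, including its normal-baseline and raised-baseline subsets, is descriptive within arm and tested only between arms;
- the maximum either does or does not include Week 22.

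SAP 6.13.10 and 6.13.8 need no change on this point. The cost is a few sentences and one set of within-arm p-values dropped. No new data are needed, and the Week 6 and Week 18 enzyme shift tables are already planned.
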